14. STATISTICAL ANALYSIS PLAN

The primary purpose of this pilot study is to evaluate the safety of baricitinib in subjects with GCA. No specific statistical hypothesis tests are planned. Safety data will be summarized for all treated subjects using appropriate tabulations, descriptive statistics, and graphical presentations. The incidence rate of each AE will be estimated and reported as number (n) and percentage (%).

Descriptive statistics will be provided for all secondary outcome measures. Differences between glucocorticoid dose (mg), C-reactive protein (mg/L), erythrocyte sedimentation rate (mm/hr) and BVAS score from baseline to end of study will be calculated and reported with means and standard deviations. The proportion of subjects in sustained remission will be reported with exact 95% confidence intervals. Kaplan-Meier methods will be used to evaluate relapse-free survival and the duration of glucocorticoid-free remission. Number of relapses per subject over time will be reported as relapses/year.

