To be enrolled, subjects must have clinically stable disease and treated with a prednisone dose of either 30 mg, 20 mg, or 10 mg (in accordance with their respective entry tier) for a minimum of 2 weeks before initiation of study drug and standardized taper. As such, the patient is not, by the physician's clinical assessment, showing signs of worsening disease (new symptoms or increasing severity of the symptoms that were observed at time of relapse) attributable to GCA. For example, a patient with relapse occurring at 30 mg prednisone may be increased to 40 mg/day for 2 weeks, 35 mg/day for 2 weeks and then 30 mg/day for two weeks. If deemed clinically stable on 30 mg/day prednisone after two weeks, the subject may enroll and begin study drug and standardized glucocorticoid taper. Additional examples: 1) if a relapse occurred at 15 mg/day, a patient may be increased to 20 mg for 2 weeks and if deemed clinically stable may undergo initiation of study drug after being on 20 mg for 2 weeks; 2) if a patient has previously been able to discontinue prednisone therapy and has a clinical relapse, prednisone can be re-initiated at 10 mg/day and if clinically stable at 2 weeks may proceed to enrollment. Once enrolled, subjects will begin study drug and reduce their prednisone dose on a standardized tapering schedule according to their respective entry dose (30 mg, 20 mg, 10 mg), as outlined in **Table 1**.

If a relapse occurs during the standardized taper (without evidence of severe ischemic event: defined as stroke, vision loss, critical limb ischemia) the patient will be removed from the standardized prednisone taper regimen but continue study drug for the remaining balance of the 52-week study period, provided no contraindication or criteria for study drug withdrawal is present at time of relapse. Once removed from the standardized prednisone taper, subsequent prednisone dose and management will be at the discretion of the treating provider. If a second relapse occurs, or if a relapse with the accompaniment of an aforementioned severe ischemic event is observed, then the study drug will be discontinued and prednisone and/or other alternative treatments will be provided as directed and at the discretion of the treating provider.

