5.3. Treatment Arms and Duration

This is an open-label, single-arm study. All subjects will receive the study drug for a maximum of 52 weeks in combination with a standardized prednisone taper.

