12.6. Time Period and Frequency for Collecting Event Information

- AEs and SAEs will be collected from the start of Study Treatment until the 12 week follow-up visit and documented at time of occurrence and each study visit.
- Medical occurrences that begin prior to the start of study treatment but after obtaining informed consent may be recorded on the Medical History/Current Medical Conditions section and will not be considered treatment related side effects.
- Any SAEs assessed as related to study participation or related to the investigational product will be recorded from the time a subject consents to participate in the study up to and including any follow-up contact.
- All SAEs will be recorded and reported to the Sponsor (Mayo Clinic) and Eli Lilly [Investigational Product (IP) Manufacturer] within 24 hours.
- Investigators are not obligated to actively seek AEs or SAEs in former study subjects (those whom have completed the study including the 12 weeks post-study drug visit). However, if the investigator learns of any SAE, including a death, at any time after a subject has been discharged from the study, and he/she considers the event reasonably related to the study treatment or study participation, the investigator must promptly notify Mayo Clinic (Sponsor) and the IP manufacturer.

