13. SAMPLE SIZE AND COMPUTATION RATIONALE

The study is intended to examine safety and to explore preliminary signal of efficacy. The sample size of 15 was based upon a sufficient number of subjects to begin such explorations prior to pursuit of a

randomized controlled trial. With an accrual of 15 evaluable subjects, there is a 95% confidence that any AE (or SAE) with an incidence of at least 18% will be reported. The standard error of the estimate of the incidence of reported AEs will not exceed 13%.

A historical cohort of patients with biopsy-proven GCA from the Mayo Clinic has recently been reported [16]. In this large single-institution cohort, we found the rate of second relapse in the subset of patients with at least one relapse was 50% at one year (or 50% relapse-free survival at one year). These relapses occurred during GC treatment performed at the discretion of the treating provider and patients were not subject to an accelerated taper, thus likely overestimating relapse-free survival at one year after initial relapse. A recent completed clinical trial evaluating the use of abatacept in GCA with standardized taper has been completed and preliminary results are available [42]. Relapse-free survival at one year in the placebo group was 31% and 48% in the treatment group. The relapse-free survival in Langford et al. study may also be slightly overestimated because all patients received three months of study drug prior to undergoing a standardized GC taper. Prior clinical trials in GCA have observed one year relapse-free survival among placebo groups to range from 10-29% [23,24,43]. With a sample size of 15 patients, an exact binomial test will have 80% power to detect an additional 37% above the expected relapse-free rate with a 0.05 one sided-significance level. Based on available clinical trial data and the preliminary results from Langford et al. [42] a conservative expected relapse-free survival in patients with relapsing GCA receiving only GC and undergoing an accelerated taper would be a 30% relapse-free survival at one year. As such, evidence of efficacy can be identified if 10 of 15 (67%) patients receiving study drug remain relapse-free during the study period.

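### The primary safety summary pools adverse events on baricitinib with events in the 12 weeks after it and ignores time on drug; a period split and person-year rates are a cheap improvement

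*Combined protocol and SAP*

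**What the plan says.** Safety over 52 weeks of baricitinib is the primary objective (sections 2 and 4).

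- **Summary measure (section 14).** "Safety data will be summarized for all treated subjects", and for adverse events "The incidence rate of each AE will be estimated and reported as number (n) and percentage". The section also allows for suitable tabulations and graphs. It names no on-treatment window, no person-time denominator and no split by period.
- **Collection window (section 12.6).** "AEs and SAEs will be collected from the start of Study Treatment until the 12 week follow-up visit". Under section 5.2 that visit falls 12 weeks after the drug is stopped for every subject, including those who stop early.
- **Exposure (section 5.3).** "All subjects will receive the study drug for a maximum of 52 weeks". Section 10.2 lists reasons for stopping sooner, among them a second relapse, a relapse with a severe ischemic event, unprovoked venous thromboembolism, laboratory limits and malignancy. After a second or severe ischemic relapse, section 5.2 says "then the study drug will be discontinued and prednisone and/or other alternative treatments will be provided".
- **Which events count.** Section 11 restricts the primary measure to events attributed to baricitinib. Section 4 has no such restriction and adds laboratory changes.
- **Precision (section 13).** The detection statement, made for 15 subjects described as evaluable, is "there is a 95% confidence that any AE (or SAE) with an incidence of at least 18% will be reported". A second statement gives the precision of an estimated incidence: "The standard error of the estimate of the incidence of reported AEs will not exceed 13" percent. Section 13 does not define evaluable and gives no time period for the 18%.

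**The concern.** A percentage of treated subjects is easy to interpret when everyone is observed for the same time on the same treatment. Here neither condition is assured. Shorter exposure lowers the percentage relative to the 52-week risk on drug. Events in the 12 weeks after the last dose, possibly under other agents, raise it. From n and % alone a reader cannot tell which effect dominates.

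This bears on the trial's primary question, and the result is meant to inform a larger randomized trial (section 5.5). Section 14 already takes time into account for secondary outcomes, with Kaplan-Meier methods for relapse-free survival and relapses per year, but not for the primary one.

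**Working it through.** **1. The plan's own figures.** With n = 15 and incidence 0.18, the probability of at least one event is 1 − 0.82^15 = 0.949. Solving for 95% gives 1 − 0.05^(1/15) = 0.181. The largest standard error is sqrt(0.25/15) = 0.129. Both stated figures, 18% and 13%, reproduce.

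**2. Share of observation spent off drug.** For a subject who stops at week t and attends the follow-up visit, the share is 12/(t + 12).

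| Drug stopped at week | Off-drug share |
|---|---|
| 52 | 12/64 = 19% |
| 26 | 12/38 = 32% |
| 12 | 12/24 = 50% |

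**3. What the crude percentage hides.** Suppose 3 of 15 subjects each have one event on drug. The crude figure is 3/15 = 20% in every row. On-drug person-years are total weeks on drug divided by 52.18. The exact 95% Poisson limits for 3 events are 0.619 and 8.767, each divided by person-years. The stopping patterns are assumptions, because the documents give no early-stop rate.

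| Assumed stopping | Weeks on drug | Person-years | Rate per 100 (exact 95% CI) |
|---|---|---|---|
| None | 780 | 14.95 | 20.1 (4.1 to 58.7) |
| 5 stop at week 26 | 650 | 12.46 | 24.1 (5.0 to 70.4) |
| 5 stop at week 12 | 580 | 11.12 | 27.0 (5.6 to 78.9) |

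**4. The 18% figure if it is read as a 52-week on-drug risk.** From section 13: relapse-free survival at one year of 30% (expected without benefit) or 67% (the efficacy mark), and a 50% one-year rate of second relapse. Assume exponential times, drug stopped only at a second relapse, and a year of 52 weeks. Let a = −ln(S) and b = ln 2 = 0.693. The chance of still being on drug at time t is e^(−at) + [a/(b − a)]·(e^(−at) − e^(−bt)). Integrating over one year gives the mean exposure, (1 − S)/a + [a/(b − a)]·[(1 − S)/a − 0.5/b].

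- S = 0.67: a = 0.400, mean 0.9645 years, total 14.5 person-years, 10% stop early.
- S = 0.30: a = 1.204, mean 0.9112 years, total 13.7 person-years, 23% stop early.

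With a constant hazard, the risk detectable with 95% probability is 1 − exp(ln 0.05/T), where T is total person-years. This is 18.7% for 14.5 and 19.7% for 13.7. An 18% risk is then seen with probability 1 − 0.82^T, or 94% and 93%. Adding assumed ischemic first relapses (up to 10%) and toxicity stops (up to 20% a year) lowers T to 11.9, which gives 22.3% and a detection probability of 91%.

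**5. The same figure over the whole collection window.** The follow-up adds 15 × 12/52 = 3.5 person-years. The range 11.9 to 14.5 becomes 15.4 to 17.9. If the same hazard applied off drug, the detectable risk would be 17.7% to 15.4%, slightly below the stated 18%.

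**The case against.** The strongest reply is that n (%) of treated subjects is an ordinary summary for an uncontrolled 15-subject pilot with no hypothesis test. Collecting events for 12 weeks after the last dose is deliberate safety follow-up. Events are documented when they occur (section 12.6) and stopping of therapy has its own form (Table 2), so the split could be made later under the general wording of section 14. Section 12.8 already relates glucocorticoid-type events to steroid exposure. Person-year rates assume a constant hazard and will be imprecise.

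Much of this stands. The follow-up is sound and the percentage should stay. But a split that is possible is not a split that is planned, and the interval widths in step 3 are a reason to show them, not to leave out the rate.

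Two stronger readings are tempting, and the documents do not support either.

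- *The 18% figure assumes that all 15 subjects complete 52 weeks.* Section 13 claims no 52-week on-drug period. The figure is a correct binomial statement about a per-subject incidence, and it holds for the planned statistic whoever completes. It moves to about 19–20% only if the quantity is changed to a 52-week on-drug risk, and counting the follow-up window moves it the other way.
- *Events on other agents will be credited to baricitinib.* Section 11 counts events attributed to the study drug, so the investigator's judgment may remove some of them. That does not settle the matter: section 4 has no such limit, section 14 tabulates each event, and attribution does not correct for unequal exposure.

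**Conclusion.** The concern holds for the summary measure. As planned, the primary safety result pools variable baricitinib exposure with 12 weeks off drug in one percentage. Off-drug time is 19% of observation for a completer and 32% for a subject stopping at week 26. An unchanged 20% can correspond to 20 or 24 events per 100 person-years on drug, depending on whether five subjects stop at week 26. The size in this trial cannot be fixed in advance, because no early-stop rate is given. Exposure loss is limited because a first relapse without a severe ischemic event does not end study drug.

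The 18% and 13% in section 13 need no correction. Read as a 52-week on-drug risk, 18% becomes about 19–20% on the documents' relapse rates alone and about 22% only with assumed ischemic and toxicity stops. Both rest on exponential times and a constant hazard. This is a worthwhile improvement to the reporting and does not undermine the design.

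**What to change.** - **Section 14.** Keep n (%) of treated subjects. Tabulate AEs and SAEs separately for on-treatment (first to last dose) and post-treatment (last dose to the 12-week visit), marking subjects who were on other agents when the post-treatment event occurred. For on-treatment events add total baricitinib person-years and events per 100 person-years with exact confidence intervals.
- **Sections 4 and 11.** Reconcile whether the primary measure counts all events or only those attributed to study drug.
- **Section 13.** Leave 18% and 13% as they are. Add that 18% is a per-treated-subject incidence over the AE collection window, and define evaluable. Note that as a 52-week on-drug risk it would be about 19–20% on the relapse rates in that section, and up to about 22% under assumed ischemic and toxicity stops.

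The cost is SAP wording and a few table columns. The data are already planned: event dates, discontinuation forms and the dosing diary (section 8.1). The downside is that person-year rates assume a constant hazard and, with 15 subjects, will have wide intervals.

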- The site must counsel the subject on the importance of maintaining the assigned visit schedule and ascertain whether or not the subject wishes to and/or should continue in the study
- In cases deemed “lost to follow-up”, the investigator must make every effort to regain contact with the subject (up to 3 phone calls to listed number and if necessary a certified letter to last known mailing address or local equivalent methods). These contact attempts will be documented in the medical record.
- Should the subject be unreachable, only then will the subject be considered to have withdrawn from the study with a primary reason of “lost to follow-up”.

Subjects who have withdrawn prematurely from the study should attend an early withdrawal visit and undergo the 12 week post-study drug follow-up period for evaluation of safety.

Subjects withdrawn prematurely from the study can be replaced by a new study entry if the study is still openly enrolling (that is has not reached enrollment of 15 subjects).

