11. STUDY ENDPOINTS

Primary endpoint:	
The primary endpoint is safety.
 
The measure by which this will be determined is the following:
 
 • Incidence of adverse events (AEs) and serious adverse events (SAEs) related to the study drug
Secondary endpoint	
The secondary endpoint preliminary efficacy of baricitinib (4mg, oral, daily) in patients with relapsing GCA.
 
The measures by which this will determined are the following:

	
 • Relapse-free survival at week 52 • Relapse-free survival at week 24 • Duration of glucocorticoid-free remission • Number of relapses per subject over time • Change from baseline erythrocyte sedimentation rate (ESR) to end of study • Change from baseline C-reactive protein to end of study • Glucocorticoid dose (mg) at week 52 compared to enrollment • Change in BVAS from baseline to end of study
--	---

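### The week-52 prednisone endpoint has no assured value for subjects whose study drug stops before about week 40, and end of study is not defined per subject for ESR, CRP and BVAS

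*Combined protocol and SAP*

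**What the plan says.** - **Prednisone.** The overview and Sections 4 and 11 fix the time point. Section 11 reads "Glucocorticoid dose (mg) at week 52 compared to enrollment".
- **ESR, CRP and BVAS.** The same sections define these as change from baseline to end of study. Section 9.12 defines that term only for the trial as a whole, as the last visit of the last subject.
- **Analysis.** Section 14 puts all four measures together as differences from baseline to end of study: "BVAS score from baseline to end of study will be calculated and reported with means and standard deviations". It names an analysis set for safety (all treated subjects) but none for efficacy. It has no rule for missing values or for values after drug stop.
- **Stopping drug.** Under Section 5.2, a first relapse without a severe ischemic event leaves the subject on drug. At a second relapse, or one with a severe ischemic event, "then the study drug will be discontinued and prednisone and/or other alternative treatments will be provided as directed". Section 10.2 adds laboratory, thromboembolic, malignancy, pregnancy, investigator and subject reasons.
- **Contacts afterwards.** Section 5.2 gives every subject, early stoppers included, a safety visit 12 weeks after the drug ends. Section 10.2 says that those who leave the study prematurely "should attend an early withdrawal visit and undergo the 12 week post-study drug follow-up period for evaluation of safety". They may be replaced while enrolment is open.
- **Forms.** Table 2 marks the Medications form at screening only.

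**The concern.** Section 2 names lower steroid requirements as a measure of preliminary efficacy, and Section 5.5 says the pilot is meant to support a possible randomized trial. If the visit schedule is followed as written, whether a week-52 dose exists depends partly on whether treatment failed. A second relapse ends study drug and leads to discretionary prednisone or other treatment. If it comes before about week 40, the last assured contact falls before week 52. After a first relapse the subject has already left the Table 1 taper, so the dose cannot be inferred from that table either. A mean over available doses would then leave out some of the subjects most likely to be taking prednisone, and more of them the worse the drug performs.

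**Working it through.** **1. The plan's own figure.** Section 13 states "With a sample size of 15 patients, an exact binomial test will have 80% power to detect an additional 37" points "above the expected relapse-free rate with a 0.05 one sided-significance level", against "30% relapse-free survival at one year". So n = 15, p0 = 0.30 and p1 = 0.30 + 0.37 = 0.67. By the exact binomial:

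- P(X ≥ 8 | 0.30) = 0.05001, just above 0.05.
- P(X ≥ 9 | 0.30) = 0.0152.
- P(X ≥ 9 | 0.67) = 0.805.

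The stated 80% is reproduced with 9 of 15. The present point does not rest on it, but 0.30 and 0.67 serve below as the pessimistic and target relapse-free rates.

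**2. The cut-off.** The last assured contact is stop week + 12. It falls before week 52 when the stop week is below 52 − 12 = 40. The ±4-day visit window (4/7 = 0.6 week) makes this 39.4 to 40.6. A subject stopped at week 20, for example, is last seen at week 32.

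**3. How many second-relapse stops fall before week 40.** Assume a constant hazard to the first on-study relapse (one-year relapse-free rate S1) and from first to second (S2). With a = −ln S1, b = −ln S2 and t = 40/52 = 0.769:

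P = 1 − [b·e^(−at) − a·e^(−bt)] / (b − a), or 1 − e^(−at)(1 + at) when a = b.

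Example with S1 = 0.30, S2 = 0.50: a = 1.2040, b = 0.6931, e^(−at) = 0.3961, e^(−bt) = 0.5867. Then P = 1 − (0.2745 − 0.7064)/(−0.5109) = 1 − 0.845 = 0.155, or 2.32 of 15.

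| S1 | S2 | P(second relapse by week 40) | Expected of 15 |
|---|---|---|---|
| 0.67 | 0.67 | 0.039 | 0.58 |
| 0.67 | 0.50 | 0.062 | 0.94 |
| 0.67 | 0.30 | 0.096 | 1.44 |
| 0.30 | 0.50 | 0.155 | 2.32 |
| 0.30 | 0.30 | 0.237 | 3.56 |

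The 0.50 is Section 13's historical figure: "rate of second relapse in the subset of patients with at least one relapse was 50% at one year". That describes patients after an initial relapse. The documents give no rate for a second relapse on study, which is why S2 is varied. They also give no expected rates for the other stopping reasons.

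**4. Effect on the mean dose.** Let k of 15 be omitted, with a week-52 mean d mg above that of the observed subjects. The all-subject mean exceeds the observed mean by k·d/15.

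- k = 1, d = 5 to 30 mg (assumed): 0.3 to 2.0 mg.
- k = 3, same d: 1.0 to 6.0 mg.
- One omitted subject at 0 mg, observed mean 1 to 3 mg (assumed): −1/15 to −3/15, so the observed mean is 0.07 to 0.2 mg too high.

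The shift in the change score is the same if omitted and observed subjects entered on similar doses.

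**5. ESR, CRP and BVAS.** Section 9.6 has ESR and CRP drawn, and Section 9.11 has BVAS scored, at every follow-up visit including the 12-week post-drug one. Values therefore exist for early stoppers. What is missing is the choice among W52, W64 (12 weeks off drug) and the subject's own last visit. As written, one mean could mix all three.

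**The case against.** Much of the case on the other side stands.

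- **A reader might infer that week-52 values cannot be obtained.** The documents do not say so. Section 5.2 stops the drug at a second relapse without saying that the subject leaves the study, and the Section 9.6 schedule to W52 makes no exception for those off drug. But the laboratory examples in Section 10.2 treat drug discontinuation as withdrawal from the study, and the only visit written specifically for early stoppers is a safety visit. Week-52 collection is unspecified, not ruled out.
- **A reader might infer that Section 14 excludes failures.** It does not prescribe a completers-only mean; it is silent. Most subjects with a single relapse stay on drug and so stay in the mean.
- **A reader might infer that the missing subjects are mainly second-relapse failures.** No figure supports this. With an assumed 10% to 20% one-year toxicity stop rate, stops before week 40 at the 67% target would total 2.0 to 3.1 of 15, of which second relapse supplies about 0.9. Under Table 1, a toxicity stopper without relapse is at 0 mg from week 22 at the latest.
- **A reader might take a larger bias.** Three missing subjects, all on 10 to 20 mg, against an observed mean of 1 to 3 mg give 3 × 7/15 = 1.4 to 3 × 19/15 = 3.8 mg. That puts every missing subject on re-treatment, which the documents do not support.
- **A reader might extend the favourable bias to ESR, CRP and BVAS.** Re-treatment after relapse could lower these by week 52, so the direction is not known.

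Finally, these are descriptive secondary endpoints in a 15-subject safety pilot. Relapse-free survival and relapses per year still show failures.

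**Conclusion.** The concern holds in a limited form. For prednisone, a named efficacy measure is fixed at week 52, yet nothing assures its collection once drug stops before about week 40. Stops for relapse would tend to make an observed-only mean too favourable, and toxicity stops at 0 mg push slightly the other way.

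The size is about 0.6 to 3.6 second-relapse stops of 15, and 0.3 to 2.0 mg for each omitted subject who is on 5 to 30 mg more than those observed. The counts rest on constant hazards and an assumed range for the second-relapse rate. The dose difference is assumed outright.

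For ESR, CRP and BVAS the finding is only that the time point is undefined per subject and could be mixed. The point should be fixed, but it does not threaten the primary safety objective.

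**What to change.** - **Sections 9.6 and 10.2:** state that every treated subject, on or off study drug and including any who are replaced, has the prednisone dose recorded at week 52, by visit, institutional record or telephone.
- **Section 14, prednisone:** analyse at week 52 in all treated subjects. Report the median and range, the number and percent on 0 mg, and the number missing with reasons. Add a sensitivity count that treats missing doses as not off prednisone. It belongs in a sensitivity analysis because it would misclassify a toxicity stopper already at 0 mg.
- **Section 14, ESR, CRP and BVAS:** define W52 as the single per-subject time point and report the number missing with reasons. Add a sensitivity analysis using the last value collected, including the 12-week post-drug visit.

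The cost is a few sentences and a record check or call for about 1 to 4 subjects at one site. No treatment rule changes. The reported steroid reduction may look slightly less favourable.
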